5.2 Changes in the Conduct of the Study or Planned Analyses

5.2.1 Changes in the Conduct of the Study

Approximately 1200 randomized participants were planned for the Part 1 analyses. During the actual study execution during the screening period for Part 1, 1293 participants were randomized into Part 1. This affects the newly randomized subject enrollment numbers anticipated for Part 2, as the number newly randomized in Part 2 will be decreased from approximately 800 to approximately 707. However, the total number randomized remains the same:

Arm	Newly Randomized Subjects in Part 2 N	Total Subjects (Randomized in Part 1 or Part 2) N	Treatment
A	472	1334	CVC 150 mg, once daily
B	235	666	Placebo, once daily

5.2.2 Changes to Analyses Prior to Database Lock

- PRO-C3 was added as a liver fibrosis measure (Section 4.2). It will be analyzed with descriptive statistics over time, including change over time and value over time.
- The Enhanced Liver Fibrosis (ELF™) Score was added as another liver fibrosis index (Section 4.2). It will be analyzed with descriptive statistics over time, including change over time, value over time, and correlation with other fibrosis indices and histological indices.
- Subgroup analyses were updated (Section 5.1.1.5). Subgroup analyses were added for NASH CRN fibrosis stage and for T2DM for the key secondary and secondary endpoints. In addition, medication use and weight loss subgroups were added, while Framingham score and smoking status were removed.

6. Data Handling and Analysis Conventions

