- At selected sites where available, non-invasive assessment of liver fibrosis by TE will be performed at Baseline (if not performed at Screening), and at Months 6 and 12.
- Pharmacokinetic samples for CVC will be collected at Months 3, 6, and 12 (pre-dose and at least 1-hour post-dose) (see Section 11.7)
- Weight, waist circumference, and hip circumference will be performed at Screening, Baseline and at Months 3, 6, and 12. Height will be performed at Screening.
- Physical examination, vital signs, and laboratory analyses (serum chemistry and hematology) will be performed at each visit. Serum immunoglobulin G (IgG), antinuclear antibody (ANA), anti-smooth muscle antibodies (SMA), anti-liver/kidney microsome type 1 (LKM1) and anti-liver cytosol type 1 (LC1) antibodies will be evaluated at Baseline. Electrocardiograms will be performed at Baseline and at Month 12.
- Adverse events and concomitant medications will be assessed at each visit.

### 7.1.2. Part 2

Part 2 of the study will focus on assessing the effect of CVC on clinical outcomes in approximately 2000 subjects, including up to 1200 subjects with a liver biopsy diagnosis of NASH and Stage 2 or 3 liver fibrosis (by NASH CRN system) previously randomized in Part 1 and an additional 800 adult subjects with a liver biopsy diagnosis of NASH and Stage 3 liver fibrosis (by NASH CRN system) newly randomized 2:1 to receive CVC or placebo in Part 2.

Subjects who remain in Part 1 at Month 12 will continue to be evaluated in Part 2 of the study and will continue the same treatment through the end of Part 2. Individual subject treatment assignments will not be revealed until the completion of Part 2 of the study.

Subjects who enter Part 2 from Part 1 of the study will have study visits every 3 months until Part 2 is completed. Study drug will be dispensed and AEs, concomitant medications, and adherence to study drug will be reviewed at every visit (every 3 months). Safety laboratory assessments will be performed every 6 months through the end of the study.

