## 8.1. Number of Subjects

### Part 1:

Part 1: Approximately 1200 subjects will be included in Part 1. They will be randomized 2:1 to the following treatment arms:

- Treatment Arm A (CVC 150 mg, once daily): approximately 800 subjects
- Treatment Arm B (placebo, once daily): approximately 400 subjects.

Subjects who remain in Part 1 at Month 12 will continue to be evaluated in Part 2 of the study and will continue the same treatment through the end of Part 2.

Part 2: Approximately 2000 subjects (including up to 1200 subjects who continue from Part 1 to Part 2) will be included in Part 2. Approximately 60% or more of subjects with Stage 3 fibrosis will be enrolled in the study overall.

- Treatment Arm A (CVC 150 mg, once daily): approximately 1334 subjects, of which approximately 534 are newly enrolled
- Treatment Arm B (placebo, once daily): approximately 666 subjects, of which approximately 266 subjects are newly enrolled

## 8.2. Inclusion Criteria: Part 1 and Part 2

For a subject to be eligible for participation in Part 1 or Part 2 of this study, *all* of the following criteria must apply.

1. Male and female subjects aged between 18 to 75 years
2. Ability to understand and sign a written informed consent form (ICF)
3. Histological evidence of NASH based on central reading of the Screening biopsy slides
  - a. Historical biopsy may be substituted for Screening period biopsy to determine eligibility if the following are met:
    - i. Historical biopsy was obtained no more than 6 months prior to the first day of screening
    - ii. Hepatic tissue is available for central histologic evaluation
    - iii. No new therapeutic intervention for NASH was made during the 6-month period (eg, obeticholic acid, vitamin E > 400 IU/day, pioglitazone, liraglutide, loss of  $\geq 7\%$  of body weight, bariatric surgery including gastric banding, investigational NASH agents)
    - iv. Subjects must have been metabolically stable since the biopsy (no significant weight loss [ $\geq 7\%$  of body weight], no major deterioration of

glycemic control, and no introduction of new or investigational drugs for the treatment of T2DM)

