5.1.1.5 Subgroup Analyses

In Part 1, subgroup analyses for the primary efficacy endpoint using the CMH test will be reported for selected subgroups to be defined in this section (table below). These analyses will place emphasis on the comparison of CVC to placebo within subgroups and assessing the consistency of magnitude of the treatment effect across subgroups. The odds ratios from the CMH analysis will be reported with associated 2-sided 95% CIs.

In addition, subgroup analyses will be conducted for the key secondary endpoint and secondary endpoints for NASH CRN fibrosis stage (2 vs. 3) and for T2DM at baseline (yes, no) (based upon the data entries in the electronic database).

Subgroup results (treatment effect estimate and two-sided 95% CIs) will be presented on a Forest plot also displaying the overall treatment effect and its 95% CI. The emphasis will be on assessing the consistency of the treatment effect across subgroups, i.e., overlapping CIs indicate consistent treatment effects.

The table below also displays the rationale for pre-specifying the specific subgroup i.e. regulatory requirements to assess consistency of effect for major demographic factors (e.g., age, sex, and race or ethnicity), [REDACTED]

[figure not shown]
For some subgroups, detailed information with many levels are collected (e.g., race/ethnicity); frequencies of subjects for each separate subgroup level will be reported as part of the demographic and baseline characteristics summaries. However, to provide an assessment of the consistency of efficacy and safety results across major subgroup categories, some levels will be combined into 3 to 4 major categories for each subgroup. This will ensure that the number of subjects per category is sufficient to perform meaningful subgroup analyses.

[figure not shown]
The list of subgroups may be modified depending on the recruitment to the trial to ensure the number of subjects is sufficient in the subgroups to be assessed. This will be determined before unblinding.

[figure not shown]
Table 5-23 Subgroups

[figure not shown]
Subgroup	Categories	Comments
Age at baseline (years)	< 65, ≥ 65	
Sex	Male, Female	
Race	White, Non-white	
NASH CRN fibrosis stage at baseline	2, 3	Data from Phase 2b to be confirmed or refuted. To be based on the true data (e.g., as reported in the CRF rather than in IxRS)

Subgroup	Categories	Comments

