- Section 5.1.1.4.3.1 Liver Biochemistry: updated section to encompass liver biochemistry elevations, not simply potential Hy’s Law or suspected drug-induced liver injuries
- Section 5.1.1.5 Subgroup Analyses: added subgroup analyses for NASH CRN fibrosis stage and T2DM for the key secondary endpoint and other secondary endpoints; clarified geographic region subgroups; removed “diabetic subjects” subset for the subgroup analyses for prior and concomitant medication use; added sodium-glucose cotransporter-2 (SGLT-2) inhibitor use and insulin use subgroups; added weight loss during the study at any time and also weight loss during the study at the liver biopsy assessment as subgroups; removed Framingham score and smoking status subgroup analyses; clarified that the length of biopsy subgroups would be based on both the baseline and Month 12 liver biopsy lengths; updated the alcohol use subgroup categories to be current drinker, former drinker, and non-drinker
- Section 5.1.1.6.1 Part 1 Analyses: clarified that the Part 1 analyses would occur when the approximately 1200 planned participants were followed through the Month 12 visit assessment; clarified that an unblinded team outside of the study team would be performing the unblinded activities through Part 2

- Section 5.2.1 Changes in the Conduct of the Study: approximately 1200 were planned but 1293 were randomized through the screening process during study execution. This would affect the numbers randomized through Part 2, but general conduct of the study is unaffected.

- Section 6.1 Study Treatment Conventions: clarified that the actual fibrosis stage and T2DM status collected via the electronic database would be used for analyses
- Section 6.2.2 Safety: clarified that plasma and serum samples collected beyond Visit 2 would still be analyzable for polymorphisms, genotype status, and pharmacogenetic biobanking
- Section 6.6.1.4 Major Adverse Cardiovascular Events (MACE): added section to describe how potential MACE cases would be identified in the AE dataset; 4-point MACE would be used, and MedDRA SMQs that would be used to identify cases were listed
- Section 6.6.1.5 Type 2 Diabetes Mellitus (T2DM): added section to describe how new onset T2DM cases would be identified in the AE dataset, along with the specific MedDRA preferred terms
- Section 6.6.2.2 Continuous Descriptive Parameters: added the ELF score and PRO-C3

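### SAP 5.1.1.5 compares CVC with placebo within subgroups defined by weight loss after randomisation; these results should be descriptive and kept apart from the baseline subgroups

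*SAP*

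**What the plan says.** SAP 5.2.2 states that "medication use and weight loss subgroups were added". That sentence does not say when weight loss is measured. The timing is in SAP section 8, in the entry for Section 5.1.1.5: the update "added weight loss during the study at any time and also weight loss during the study at the liver biopsy assessment as subgroups". The two statements agree, and section 8 is used here only for the timing.

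For the analysis itself, SAP 5.1.1.5 says that "subgroup analyses for the primary efficacy endpoint using the CMH test will be reported for selected subgroups" and that "These analyses will place emphasis on the comparison of CVC to placebo within subgroups". Odds ratios with 95% confidence intervals go on a forest plot beside the overall effect, under the reading rule that "overlapping CIs indicate consistent treatment effects". The visible text does not separate baseline from post-baseline subgroups.

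The visible rows of Table 5-23 (age, sex, race, fibrosis stage, region) are all baseline factors. The weight-loss rows are redacted, as is part of the sentence giving the rationale for the subgroups. The cut-offs and any comment beside them cannot be read.

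**The concern.** A subgroup comparison inherits the protection of randomisation only if membership is fixed before treatment starts. Weight loss during the study is not. If CVC changes who loses weight, the CVC and placebo patients who lose weight are selected differently, and so are those who do not. If weight loss also shares causes with histologic response, the arms then differ in prognosis within each subgroup even when CVC has no effect on response.

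The trial's own documents support the second condition. Protocol 8.2, inclusion criterion 3a, requires for a historical biopsy that "No new therapeutic intervention for NASH was made during the 6-month period", and loss of at least 7% of body weight is among the examples that follow. SAP 5.1.1.1.5 expects weight change to Month 12 to be an explanatory variable when the Part 1 primary endpoint is imputed.

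What is at stake is how exploratory results are read. Shown in the same plot as age or fibrosis stage, a weight-loss row looks like evidence on whether the effect differs between kinds of patient, or is the same in both. It can support neither conclusion.

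**Working it through.** The plan states no figure on this point, so there is none to reproduce. The check has four steps.

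**1. Timing.** For Part 1, Protocol 7.1.1 says "Weight, waist circumference, and hip circumference will be performed at Screening, Baseline and at Months 3, 6, and 12". The Month 3, 6 and 12 values are on treatment, so both weight-loss definitions in SAP section 8 depend on data collected after randomisation.

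**2. One worked scenario, no effect of CVC on response.** All inputs are assumptions, because the documents give no weight-loss rates. An unmeasured factor is present in 30% of subjects. It raises response from 12% to 30% and gives a 50% chance of weight loss in either arm. In the other 70%, weight loss is 10% on placebo and 20% on CVC.

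- Overall response, both arms: 0.12 + 0.18 × 0.30 = 17.4%, so the true OR is 1.00.
- Weight loss: placebo 0.30 × 0.50 + 0.70 × 0.10 = 0.22; CVC 0.30 × 0.50 + 0.70 × 0.20 = 0.29.
- Share with the factor among losers: placebo 0.15/0.22 = 0.682; CVC 0.15/0.29 = 0.517.
- Response among losers: placebo 0.12 + 0.18 × 0.682 = 24.3%; CVC 0.12 + 0.18 × 0.517 = 21.3%. OR about 0.84.
- Among non-losers the shares are 0.15/0.78 = 0.192 and 0.15/0.71 = 0.211. Response is 15.5% and 15.8%, OR about 1.03.

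**3. A range of scenarios, again with no effect of CVC on response.** Assumptions: the unmeasured factor has 50% prevalence and the same odds ratio (3 or 6) on weight loss and on response; placebo weight loss is 15% or 25%; placebo response is 15% (the planning rate in SAP 5.1.2). Within each arm and subgroup, response = Σ P(u)·P(weight-loss status given u, arm)·P(response given u) divided by Σ P(u)·P(weight-loss status given u, arm).

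| CVC effect on odds of weight loss | OR for response, losers | OR for response, non-losers |
|---|---|---|
| none | 1.00 | 1.00 |
| halved | 1.01 to 1.03 | 1.02 to 1.07 |
| × 1.5 | 0.97 to 0.99 | 0.95 to 0.98 |
| × 2 | 0.95 to 0.98 | 0.90 to 0.97 |
| × 3 | 0.92 to 0.96 | 0.84 to 0.95 |

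The two extremes both come from 25% placebo weight loss and a factor OR of 6. With the odds tripled (45.8% weight loss on CVC), response among non-losers is 13.0% on placebo and 11.2% on CVC. With the odds halved (15.1% on CVC), it is 13.0% and 13.9%.

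The opposite error is also possible. Suppose response is 35% with weight loss and 10% without, whatever the arm, and CVC raises weight loss from 20% to 40%. Overall response is 0.20 × 0.35 + 0.80 × 0.10 = 15% on placebo and 0.40 × 0.35 + 0.60 × 0.10 = 20% on CVC. That is a real 5-point benefit, yet the difference is zero in both subgroups.

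**4. Subjects without an evaluable Month 12 biopsy.** SAP 5.1.2 expects 15%, counted as nonresponders: 0.15 × 1200 = 180, or 0.15 × 1293 = 194 of those randomised (SAP 5.2.1). This figure mixes subjects with no biopsy and subjects with an unreadable one. Those with no biopsy have no weight at a biopsy assessment, and the visible text does not say which subgroup they enter. Under the at-any-time definition, early dropouts have fewer visits at which to be classed as losing weight. Membership is therefore tied to how the outcome is ascertained.

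**The case against.** The strongest reply is that these are exploratory analyses outside the testing hierarchy (SAP 5.1.1.3.1) and the alpha procedure (SAP 5.1.1.3.3), meant only to assess consistency. That stands. A reader might infer that the trial's randomisation is broken or its primary result compromised; the documents do not support that, since the mITT comparison uses all dosed subjects as randomised.

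A second reply is that the scenario in step 2 would raise no alarm under the SAP's own rule. With 400 and 800 subjects, the losers number 88 and 232 (OR 0.84, 95% CI about 0.47 to 1.51), the non-losers 312 and 568 (OR 1.03, about 0.70 to 1.50), and the overall OR is 1.00 (about 0.73 to 1.37). The intervals overlap, so the result would be read as consistent. That also stands: one cannot say that a false signal of effect modification will appear. It does not rescue the analysis, because a reading of consistency from a non-randomised comparison is no better founded, as the mediation example shows.

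Third, nothing visible in the documents shows that CVC affects weight; if it does not, the bias in these scenarios is zero. Fourth, the redacted rows may carry a caveat, so the use of the common method for weight loss is inferred from the general text. Fifth, whether response differs by weight loss is a fair exploratory question. All three limit the strength of the point, but none gives a reason to put the comparison beside baseline subgroups.

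A reader might also extend the criticism to every medication-use subgroup. The documents do not support this. SAP section 8 lists use of GLP-1 analogues, SGLT-2 inhibitors and insulin among baseline characteristics. It also refers to prior and concomitant use for the subgroups, but the definitions are redacted. Only a subgroup defined by use started after randomisation has the same problem.

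**Conclusion.** The point holds in a limited form. As far as the text can be read, the SAP compares CVC with placebo on the Part 1 primary endpoint within two subgroups defined after randomisation, by a variable its own documents link to the disease and the endpoint. Those within-subgroup comparisons lack the protection of randomisation. The primary comparison, the alpha and the sample size are untouched.

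Neither the direction nor the size of any bias is known. The within-subgroup odds ratio of about 0.84 to 1.07 under no true effect rests on assumed weight-loss rates and an assumed unmeasured factor, and it includes no bias at all. This is a low-cost improvement to the interpretation of exploratory results. It is conditional on the redacted rows of Table 5-23 not already containing the distinction.

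**What to change.** In SAP 5.1.1.5 and Table 5-23, restrict the CVC-versus-placebo CMH analyses and the forest plot to variables fixed at baseline, including medication use at baseline. Report on-study weight loss at any time and at the biopsy in a separate display by arm, labelled as post-randomisation and non-causal, and state that the overlapping-interval rule does not apply to it. Treat in the same way any medication subgroup defined by use started after randomisation. State how subjects without a biopsy, and those who leave early, are classified in that display.

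The cost is SAP wording, to be settled before Part 1 unblinding. Section 5.1.1.5 already foresees changes to the subgroup list up to that time, although for reasons of subgroup size. Two exploratory comparisons become descriptive. Little information is lost, because SAP 5.1.1.4.4 and 6.6.3 already summarise weight by arm and define weight-change categories.

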6.1 Study Treatment Conventions

Treatment assignment will be done using permuted block randomization via IxRS stratified by NASH CRN fibrosis stage (2 or 3) and presence or absence of documented T2DM (yes or no). In case of discordance of the assignment of randomization strata between IxRS and EDC, the true fibrosis stage and T2DM status at baseline will be used for the analysis.

6.1.1 Analysis Days

Treatment days are defined as follows:

Table 6-1 Analysis Day Definitions

Term	Description
Treatment Day	Relative to treatment start date If analysis date \geq treatment start date: 
• Day = analysis date – treatment start date + 1
○ Day 1 = treatment start date If analysis date < treatment start date: 
• Day = analysis date – treatment start date
○ Day -1 = day before treatment start date○ There is no Day 0

6.1.2 Missing/Incomplete Treatment End Date

If the investigator is unable to provide the treatment end date, the last available dosing record date will be used as treatment end date.

6.2 Analysis Visit Windows

6.2.1 Efficacy

The analysis visit windows for efficacy endpoints, including liver biopsy, are defined as follows:

Table 6-2 Efficacy Analysis Visit Definitions

Analysis Phase	Analysis Visit (Derived)	Study Visit (eCRF)	Window
Part 1 & Part 2			
Pretreatment	Baseline	Day 1	Treatment Day ≤ 1 , pre-randomization in Part Y
Treatment	Month 12	Day 360	Treatment Day [316, 405], post-randomization in Part 2 Note: For the primary efficacy analysis in Part 1 using the mITT analysis set, any available liver biopsy after randomization will be used for the Month 12 biopsy, no matter when it was obtained relative to the first dose of study drug. Subjects with multiple liver biopsies will have the evaluable biopsy closest to the Month 12 visit included in the analysis.
	Month 60	Day 1800	Treatment Day [1756, 1845], post-dose in Part 2
	End of study	Final or termination visit	Last non-missing assessment during the Treatment Period in Part Y / between Treatment Day 1 in Part Y, post-dose, and Off-treatment Day 1, inclusive, where Y=1, 2.

The following general conventions for repeated or unscheduled assessments will apply unless otherwise specified:

- For scheduled and unscheduled assessments, if more than one assessment is measured within the same visit window, then the record with the latest visit date (from baseline) will be used for that visit window.
- All assessments will be included in respective listings.

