### **12.1.4. Handling of Missing Data**

Data will be analyzed as recorded. Results will be used in the analysis as obtained, without regard for any visit windows. Subjects with missing baseline biopsy data should not be randomized in the study; in the unlikely event that any such subject is incorrectly randomized into the study, the subject will be excluded from analyses (including ITT) due to lack of data for stratification. Such subjects will be listed.

For the primary efficacy analysis in Part 1 using the mITT analysis set, any available liver biopsy after randomization will be used for the Month 12 biopsy, no matter when it was

obtained relative to the first dose of study drug. Subjects with multiple liver biopsies will have the evaluable biopsy closest to the Month 12 visit included in the analysis. Subjects who do not have an evaluable liver biopsy at both Screening and Month 12 will be included in the analyses as non-responders. Summaries of subjects who do and who do not have evaluable liver biopsies at Month 12 will be provided to assess whether demographics, baseline data or safety data are predictive of missingness. Sensitivity analyses for the primary efficacy endpoint will be performed, accounting for both missing at random and missing not at random scenarios.

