5.1.1.1 Common Conventions

5.1.1.1.1 Analysis Populations

The analysis populations will consist of subjects as defined below:

Table 5-1 Analysis Populations

Population	Definition	Study Treatment
Screened	All screened subjects who sign informed consent.	—
Intent-to-Treat (ITT)	All randomized subjects will be included in the randomly assigned treatment group, even if they receive a different treatment from that to which they are randomly assigned. This will be a supportive analysis set for selected efficacy analyses. Subjects with missing Screening biopsy data should not be randomized in the study, and hence will not be included in the ITT analysis set, should such subjects exist.	Randomized assignment
Modified Intent-to-Treat (mITT)	All randomized subjects who receive ≥ 1 dose of study drug will be included in the randomly assigned treatment group, even if they receive a different treatment from that to which they are randomly assigned. This will be the primary analysis set for the efficacy analyses.	Randomized assignment
Month 12 per protocol (PP1)	All subjects randomly assigned to a treatment group who have an evaluable biopsy at Screening and another after at least 6 months but before 15 months of follow-up, receive at least 6 months of assigned study drug and have no significant protocol deviations that potentially influence the primary efficacy assessment will be included in the PP1 analysis set. This will be a supportive analysis set for selected efficacy analyses of Part 1 and Part 2.	Randomized assignment

Population	Definition	Study Treatment

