Part 1: Primary efficacy endpoint (sensitivity analyses 1)	The primary efficacy endpoint will be performed using the ITT and PP1 populations as sensitivity analyses.	Same as above	Cochran-Mantel-Haenszel (CMH) test, stratified by actual fibrosis stage (2, 3) and T2DM status (presence, absence) at baseline
Part 1: Primary efficacy endpoint (sensitivity analysis 2)	Logistic regression, with fibrosis stage, presence of T2DM, study site as predictors and baseline covariates (to be listed out later) using the mITT analysis set.	Same as above	Logistic regression, with covariates for the stratification factors
Part 1: Primary efficacy endpoint (sensitivity analysis 3)	An assessment of efficacy will also be made using multiple imputation, for scenarios of both assuming missing at random and missing not at random, for the CMH test. Refer to Section 5.1.1.1.5.	Same as above	Multiple imputation

[figure not shown]
Type of Endpoint	Description	Timing	Methodology
Part 1: Primary efficacy endpoint (subgroup analysis)	Refer to Section 5.1.1.5.	Same as above	Cochran-Mantel-Haenszel (CMH) test, stratified by true fibrosis stage (2, 3) and T2DM status (presence, absence) at baseline
Part 1: Secondary efficacy endpoints (binary)	Analysis of other secondary efficacy endpoints of Part 1 will use similar methods to the primary endpoint analysis. Results for the mITT and PP1 analysis sets will be reported for secondary efficacy endpoints.	Same as above	Cochran-Mantel-Haenszel (CMH) test, stratified by true fibrosis stage (2, 3) and T2DM status (presence, absence) at baseline
Part 1: Secondary efficacy endpoints (continuous)	Continuous endpoints will be analyzed with analysis of covariance, with true fibrosis stage (2, 3) and T2DM status (presence, absence) at baseline) included as factors using the mITT and PP1 populations.	Same as above	CFB ANCOVA

[figure not shown]

Type of Endpoint	Description	Timing	Methodology

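### SAP Table 6-2 puts a Day 316-405 window on Month 12 biopsies and lifts it only for the Part 1 primary analysis in mITT, contradicting Protocol 12.1.4, the PP1 definition and SAP Table 5-4

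*SAP*

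**What the plan says.** - **SAP 6.2.1, Table 6-2.** The scope is wide: "The analysis visit windows for efficacy endpoints, including liver biopsy, are defined as follows". The Month 12 row reads "Treatment Day [316, 405], post-randomization in Part 2", and Month 60 is Days 1756-1845. A Note in the Month 12 row lifts the window for one analysis: "For the primary efficacy analysis in Part 1 using the mITT analysis set, any available liver biopsy after randomization will be used", taking the evaluable biopsy closest to Month 12. Below the table, when several records fall in one window, the latest is used.
- **Protocol 12.1.4.** The general rule is "Results will be used in the analysis as obtained, without regard for any visit windows". The any-available-biopsy rule for the Part 1 primary analysis follows it.
- **PP1 (Protocol 12.1.1; SAP Table 5-1).** Besides the Screening biopsy, a subject needs "another after at least 6 months but before 15 months of follow-up".
- **SAP 5.1.1.1.5, Table 5-4.** For the Part 1 primary endpoint, any adequate post-baseline biopsy serves for the target visit, whenever obtained. A subject lacks an evaluable biopsy only if there is none after baseline or the central reader could not evaluate it. The same rule is carried to the Month 60 responder endpoint. No row covers Month 12 in subjects newly randomised in Part 2.
- **SAP 5.1.1.3.1, Table 5-14.** "The primary efficacy endpoint will be performed using the ITT and PP1 populations as sensitivity analyses". For the Part 1 secondary endpoints: "Analysis of other secondary efficacy endpoints of Part 1 will use similar methods to the primary endpoint analysis". Part 2 secondary endpoints are tied in like terms to the Part 2 primary analysis.

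**The concern.** Which biopsy counts as the Month 12 biopsy determines every histology result. Read literally, Table 6-2 lets a Day 200 biopsy count in the mITT primary analysis but gives the same subject no Month 12 value in the ITT or PP1 run of that endpoint. In PP1 this defeats itself, because that biopsy is what admits the subject.

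The affected biopsies are not a random sample. They come from subjects who left the study early after at least 6 months on drug, for whom a biopsy is asked for where feasible (Protocol 11.2), and from late biopsies. Both could differ by arm.

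The at-least-2-stage endpoint is the global key secondary and the EU Part 1 primary (SAP 4.2), and SAP 5.1.1.3.3 makes the larger Part 2 alpha depend on the key secondary as well as the primary. Two programmers could follow different sentences of the SAP and obtain different results.

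**Working it through.** **1. Which analyses have an explicit exemption from the window?**

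| Analysis | Text that could lift the window | Explicit? |
|---|---|---|
| Part 1 primary, mITT | Table 6-2 Note; Table 5-4 | Yes |
| Part 1 primary, ITT and PP1 | Table 5-14 reruns the endpoint in these sets; the Note names mITT only | No |
| Part 1 key secondary | Analysed with the primary in Table 5-14; same non-response rule in Table 5-3 | By inference |
| Part 1 other secondaries | Similar-methods sentence; biopsy selection not mentioned | By inference |
| Month 12, newly randomised in Part 2 | Similar to the Part 2 primary; no row in Table 5-4 | No |
| Month 60 responder | Table 5-4 says any biopsy; Table 6-2 sets Days 1756-1845 without a Note | Contradictory |

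The Month 12 row sits under a header covering both parts, yet its wording refers to randomisation in Part 2, so its reach into Part 1 is itself unclear.

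**2. Day arithmetic** (the SAP's 30-day months, target Day 360).
- Table 6-2 window: 405 - 316 + 1 = 90 days.
- PP1 range, at least 6 and before 15 months: Days 180-449, 449 - 180 + 1 = 270 days.
- In PP1 but outside the window: Days 180-315 (136 days) and 406-449 (44 days).
- Scheduled biopsy, within 2 weeks: 360 - 14 to 360 + 14, Days 346-374, all inside the window.

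Calendar months move the PP1 limits by a few days and change nothing. These are counts of days, not of biopsies.

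**3. Tie rule.** Take hypothetical biopsies on Days 340 and 400. The closest to Day 360 is Day 340 (20 days against 40); the latest in the window is Day 400. The two rules select different slides.

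**4. The plan's power figures** (SAP 5.1.2: 800 against 400, 2-sided alpha 0.0012, z = 3.239). With unpooled variance, power = Φ(|p1 - p2| / SE - z), SE = √(p1(1-p1)/n1 + p2(1-p2)/n2).
- Primary, 25% against 15%: SE = 0.02352, 0.10/0.02352 = 4.252, power 84.4% (stated 84%).
- Key secondary, 8.6% against 2.2%: SE = 0.01233, 0.064/0.01233 = 5.190, power 97.4% (stated 97%).

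Pooled null variance gives 78% and 89%, so the unpooled form is used below.

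**5. Illustration for the at-least-2-stage endpoint.** SAP 5.2.1 reports 1293 randomised in Part 1 and reduces the new Part 2 numbers to 472 and 235. Part 1 is then 1334 - 472 = 862 and 666 - 235 = 431. Assume a share w of biopsies in both arms is out of window and scored non-responder, so that each rate is multiplied by (1 - w).

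| w | CVC | Placebo | Power at 0.0012 |
|---|---|---|---|
| 0 | 8.60% | 2.20% | 98.4% |
| 5% | 8.17% | 2.09% | 97.7% |
| 10% | 7.74% | 1.98% | 96.8% |
| 15% | 7.31% | 1.87% | 95.6% |

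The documents give no value for w; the range is an assumption.

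**The case against.** The best reply is that the SAP already has a controlling rule. Table 5-4 is written for a generic target visit, extends the any-biopsy rule to a secondary endpoint at Month 60, and does not treat an out-of-window biopsy as non-evaluable. The general responder method in Table 5-2 refers missing or inadequate biopsies to that section. The key secondary shares the primary's analysis sentence and estimand, and the other secondaries are tied to the primary analyses. On this reading Table 6-2 never bites on biopsy.

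Much of that stands. A reader might infer that the other Month 12 analyses will lose valid biopsies and score those subjects as non-responders; the documents do not establish this. Nor do they make exit biopsies mandatory, and the 180 of 270 days outside the window do not mean that two thirds of biopsies are affected.

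The reply does not remove the conflict. Table 6-2 names liver biopsy in its scope, and an exemption limited to one analysis set implies that the window applies elsewhere. The similar-methods sentences do not mention biopsy selection, and nothing explicit covers the ITT and PP1 runs or Month 12 in the new Part 2 subjects. SAP 5.2.2, which lists changes to the analyses, does not mention a departure from the protocol's no-window rule.

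**Conclusion.** The contradiction is real and should be resolved. For the ITT and PP1 runs and for Month 12 in newly randomised Part 2 subjects, the only explicit timing rule is the window. For the key secondary, the other secondaries and Month 60, the SAP supports two readings. The Part 1 primary analysis in mITT is protected.

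The size cannot be fixed. On-schedule biopsies are safe, and the share of early-exit and late ones is not stated. Under the assumed equal loss of 5% to 15% in both arms, the loss of power for the at-least-2-stage endpoint is 0.7 to 2.8 points (98.4% to 97.7% and to 95.6%). Unequal loss between arms is not covered by that range. No power should be quoted for PP1, which is a supportive set with no assigned alpha. The case rests on the conflicting rules, not on the power figures.

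**What to change.** Before Part 1 unblinding, amend SAP Table 6-2 to state that:

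1. the analysis windows and the latest-record rule do not apply to liver biopsy;
2. every Month 12 and Month 60 histology endpoint in mITT and ITT, in both parts, uses the evaluable post-baseline biopsy closest to the target visit;
3. Month 12 analyses in PP1 use the evaluable biopsy closest to Month 12 within PP1's own limits of at least 6 and before 15 months;
4. the Table 6-2 windows apply only to non-biopsy efficacy assessments.

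The cost is SAP wording and one programming rule. No new data are needed.
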